## 9 Measurement of Effect

Participants will be assessed by RECIST version 1.1 criteria. For the purposes of this study, participants should be reevaluated every 8 weeks. In addition to a baseline scan, confirmatory scans should also be obtained  $\geq 4$  weeks following initial documentation of an objective response. If a confirmation scan is performed within 2 weeks of a regularly scheduled scan, then the regularly scheduled scan can be delayed until the next required time point. In practice, the confirmation scan will likely be obtained 8 weeks after the original responsive scan, concurrent with the next scheduled radiographic assessment.

### 9.1 Antitumor Effect– Solid Tumors

Response and progression will be evaluated in this study using the new international criteria proposed by the Response Evaluation Criteria in Solid Tumors (RECIST) ([Eisenhauer et al, 2009](#)) guideline. Changes in the diameter (unidimensional measurement) of the tumor lesions are used in the RECIST criteria.

#### 9.1.1 Definitions

Evaluable for toxicity. All participants who receive at least one dose of study treatment will be evaluable for toxicity from the time of their first treatment.

Evaluable for objective response. Only those participants who have measurable disease present at baseline, have received at least one cycle of therapy, and have had their disease re-evaluated will be considered evaluable for response. These participants will have their response classified according to the definitions stated below. (Note: Participants who exhibit objective disease progression or die prior to the end of cycle 1 will also be considered evaluable.)

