### **1.4 Primary Endpoint**

- The primary efficacy endpoint is ORR, defined as partial response (PR) or complete response (CR), occurring at any point post treatment according to RECIST (version 1.1) criteria.

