- 7 PK samples will be collected pre-dose on Cycle 1 Day 1 and Cycle 2 Day 1. Additional PK samples will be collected on Cycle 1 Day 1 only at the following time-points: 1, 2, and 4 hours ( $\pm$ 10 minutes), and 6 and 8 hrs ( $\pm$ 20 minutes) post dose. Whole blood will be collected in EDTA-K2 tubes (lavender top). Refer to site-specific laboratory manual for further details.
- 8 Disease assessments will initially be performed at 8 week intervals (after cycle 2 [at the beginning of cycle 3 in the table above], after cycle 4 [at the beginning of cycle 5], and so on until cycle 11). From cycle 11 forward, disease assessments will be performed at 12 week intervals (after cycle 13 [at the beginning of cycle 14] and so on). Disease assessments may be limited to the sites of disease. RECIST-defined responses will be confirmed with a repeat assessment in  $\geq$ 4 weeks (See [Section 9](#)). Disease assessments will also be performed at the End of Treatment.
- 9 Any participant who discontinued study treatment for any reason other than disease progression, death or withdrawal of consent will continue to have disease assessments every 12 weeks ( $\pm$ 14 days) until the participant starts another anti-cancer therapy.
- 10 From cycle 11 forward, study visits will be every 6 weeks but disease assessments will be every 12 weeks (after cycle 13, 16, etc).
- 11 Baseline procedures are to be obtained within 14 days of the start of study treatment with the exception of obtaining informed consent and baseline disease assessments, which should be obtained within 28 days prior to the start of study treatment.
- 12 All assessments and procedures (with the exception of baseline) have a  $+$ - 3 day window.

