### **For Participants with Measurable Disease (i.e., Target Disease)**

Target Lesions	Non-Target Lesions	New Lesions	Overall Response	Best Overall Response for when Confirmation is Required:
CR	CR	No	CR	$\geq 4$ wks confirmation
CR	Non-CR/Non-PD	No	PR	$\geq 4$ wks confirmation
CR	Not evaluated	No	PR	$\geq 4$ wks confirmation
PR	Non-CR/Non-PD/Not evaluated	No	PR	
SD	Non-CR/Non-PD/Not evaluated	No	SD	Documented at least once $\geq 4$ wks from baseline
PD	Any	Yes or No	PD	No prior SD, PR or CR
Any	PD*	Yes or No	PD	
Any	Any	Yes	PD	

\* In exceptional circumstances, unequivocal progression in non-target lesions may be accepted as disease progression.

Note: Participants with a global deterioration of health status requiring discontinuation of treatment without objective evidence of disease progression at that time should be reported as "*symptomatic deterioration*". Every effort should be made to document the objective progression even after discontinuation of treatment.

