### **13 Statistical Considerations**

#### **13.1 Study Design/Endpoints**

This study will enroll patients with advanced (stage IIIB or IV) NSCLC harboring RET translocations. Participants will receive oral ponatinib on an open-label basis, undergoing radiographic assessments of response every 2 cycles. After a participant has completed 10 cycles, disease assessments will be performed at three cycle intervals. Response will be scored by RECIST criteria and consist of partial responses and complete responses. Treatment with

ponatinib will continue until disease progression, unacceptable toxicity, participant withdrawal, death or discontinuation from the study for any other reason. Participants will be allowed to continue receiving ponatinib despite progressive disease if they are deriving clinical benefit.

In order to investigate the preliminary efficacy of ponatinib, the primary endpoint for this cohort is the overall response rate using RECIST criteria. If at least 4 of 20 participants were to achieve a complete or partial response, ponatinib will be considered to have promising clinical activity in this molecularly defined population. The decision rule is associated with 89% power if 30% of patients in the targeted population truly were to have tumors responsive to ponatinib. In contrast, the probability of type 1 error is only 13% if the underlying rate of overall response were 10%, indicating a minimal level of anti-tumor activity. A relatively high rate of overall response is assumed under the alternative hypothesis, as ponatinib is an inhibitor against a molecular target.

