### **13.2 Sample Size/Accrual rate**

RET translocations are present in approximately 1-2% of patients with NSCLC. We expect to enroll approximately 1 participant per month between Massachusetts General Hospital, Yale New Haven Hospital and UC Irvine Douglas Hospital. This estimate is in keeping with accrual rates for other trials involving NSCLC patients with mutations (e.g. ROS1) present at a rate of 1%. Thus, we would complete enrollment of 20 patients in approximately 2 years.

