#### **13.3.3 Safety**

Toxicity will be assessed using CTC v4.0 criteria. All participants who receive any amount of study drug will be evaluable for toxicity.

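### Section 9.1.1 drops treated participants who are nearly all non-responders from the response-evaluable set, and Section 13.1 does not say whether the primary ORR uses that set; if it does, the ORR is likely biased upward by a modest amount

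*Combined protocol and SAP*

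**What the plan says.** Section 9.1.1 gives the only response population in the documents: "Only those participants who have measurable disease present at baseline, have received at least one cycle of therapy, and have had their disease re-evaluated" are evaluable for response. Its note adds: "Participants who exhibit objective disease progression or die prior to the end of cycle 1 will also be considered evaluable".

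The primary endpoint in Section 1.4 carries no denominator: "The primary efficacy endpoint is ORR, defined as partial response (PR) or complete response (CR), occurring at any point post treatment". Section 13.1 states the decision rule as a count: "If at least 4 of 20 participants were to achieve a complete or partial response, ponatinib will be considered to have promising clinical activity". It gives 89% power at a true response rate of 30% and 13% type I error at 10%. Section 13.2 sets the size: "Thus, we would complete enrollment of 20 patients in approximately 2 years". Neither section refers to 9.1.1, names a response population, or says how an unevaluable participant is counted. Section 13.3.3 does name a population, but for toxicity only: "All participants who receive any amount of study drug will be evaluable for toxicity".

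Three other provisions bear on who is left out:

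- Footnote 8 to Table 8-1 sets the scan timing: "Disease assessments will initially be performed at 8 week intervals". The first scheduled scan therefore falls after cycle 2.
- The note under the best-response table in Section 9.1.3 gives symptomatic deterioration its own label: "Participants with a global deterioration of health status requiring discontinuation of treatment without objective evidence of disease progression at that time".
- Section 5.1 (item 18) requires imaging at End of Treatment, and Section 5.8 foresees participants who do not come back for it.

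**The concern.** ORR is the primary endpoint of a single-arm trial, so its denominator should be fixed before any data are seen. The plan defines a restricted response set and then does not say whether the primary analysis uses it. After the data are in, an analyst could defend either 20 or a smaller number.

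The choice is not neutral, because the restriction depends on early toxicity, withdrawal and clinical decline. The participants it removes have almost no chance of a documented response, so they leave the denominator while the numerator stays the same. The note in 9.1.1 also creates an unexplained asymmetry: a death in cycle 1 is kept as a non-response, but a death in cycle 2 before any scan is dropped.

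There is a second, smaller inconsistency. Section 1.4 counts a response at any time after treatment, whereas 9.1.1 would discard a confirmed response in someone who received less than one cycle.

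**Working it through.** **Inputs.** The decision rule (at least 4 of 20), the null rate of 10%, the alternative of 30%, and the stated 13% and 89% come from Section 13.1. The enrolment of 20 comes from Section 13.2. The evaluable set and its note come from Section 9.1.1. The documents give no rate of non-evaluability, so I assume 1, 2 or 3 of 20 are lost, all non-responders.

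**Step 1: reproduce the plan's figures.** With X binomial(20, p), P(X ≥ 4) = 1 − [P(0) + P(1) + P(2) + P(3)].

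- p = 0.10: 1 − (0.12158 + 0.27017 + 0.28518 + 0.19012) = 1 − 0.86705 = 0.1330, stated as 13%.
- p = 0.30: 1 − (0.00080 + 0.00684 + 0.02785 + 0.07160) = 1 − 0.10709 = 0.8929, stated as 89%.

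Both agree, so the stated operating characteristics belong to a denominator of 20.

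**Step 2: who falls outside the 9.1.1 set.**

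| Treated participant | In the 9.1.1 set? |
|---|---|
| Objective progression or death before the end of cycle 1 | Yes, by the note |
| Stops in cycle 1 for toxicity, withdrawal or symptomatic deterioration, no objective progression by then | No: less than one cycle, and the note does not apply |
| Completes cycle 1, then dies or is lost before any scan | No: not re-evaluated, and the note ends with cycle 1 |
| Completes cycle 1 and is re-evaluated | Yes |

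The measurable-disease condition removes no eligible participant, because Section 3.1.5 already requires it for entry.

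**Step 3: effect on the estimate.** With r responders among 20 and k non-responders removed, the ORR moves from r/20 to r/(20 − k).

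| Removed (k) | Denominator | r = 4 | r = 6 |
|---|---|---|---|
| 0 | 20 | 20.0% | 30.0% |
| 1 | 19 | 21.1% | 31.6% |
| 2 | 18 | 22.2% | 33.3% |
| 3 | 17 | 23.5% | 35.3% |

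The shift runs from 1.1 points (21.1 − 20.0) to 5.3 points (35.3 − 30.0).

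**Step 4: effect on the decision rule.** If all 20 are counted and unevaluable participants are non-responders, the responder count does not change. P(X ≥ 4) is then as in Step 1: 13.3% and 89.3%.

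**The case against.** The strongest reply is that the plan already points to all 20. The rule is a count out of 20, enrolment is 20, the stated error rates reproduce on 20, and no passage gives a rule based on evaluable participants. This stands as the more natural reading, and it protects the decision rule. It does not settle the reported ORR, because 9.1.1 says in terms who alone is evaluable for response and Section 13.1 does not override it.

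The excluded group is also narrow. An End of Treatment scan is due within 14 days of the last dose (Section 5.5), and every effort is to be made to complete those assessments (Section 5.8). Participants who stop for reasons other than progression, death or withdrawal of consent are scanned every 12 weeks until new therapy (Section 5.7). The symptomatic-deterioration note asks for later documentation of progression. Section 7.3 provides for dose interruption before discontinuation for much toxicity. Section 2.1 reports vascular occlusion within 2 weeks of starting, but a phase 1 median onset of 5 months. All of this limits the size of the bias. It does not waive the one-cycle condition, and it does not reach participants who die or are lost before a scan.

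A reader might infer more than the documents support:

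- **That the go decision is compromised.** Step 4 shows it is not when all 20 are counted.
- **That replacing unevaluable participants inflates the type I error.** The plan contains no provision to replace treated participants.
- **That the rule means 20% of evaluable participants, or that losses unrelated to response erode power.** Neither has a basis in the text. Even on the percentage reading, the cut-off stays at 4 for 16 to 20 evaluable.
- **That a planned confidence interval is distorted.** Section 13 specifies none for ORR.

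**Conclusion.** The point holds as an unspecified primary denominator, with a likely upward bias if 9.1.1 is applied as written. It does not show an error in the decision rule.

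The bias is modest: 1.1 to 5.3 percentage points for 1 to 3 lost non-responders with 4 or 6 responders. For scale, the exact 95% interval around 4 of 20 (my calculation, not planned in the protocol) runs from 5.7% to 43.7%.

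The size rests on the assumed losses, and the direction rests on the excluded participants being non-responders. That is very likely but not certain. Someone who stops in cycle 1 for toxicity is still scanned and could have a confirmed response. If 5 of 20 responded (25.0%) and one responder and one non-responder were excluded, the result would be 4/18 = 22.2%. That case is remote, but it too argues against the 9.1.1 set as the primary denominator.

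Confidence is high that the denominator is unstated, and lower that the bias would be material in practice. The change is still worth making, because it concerns the primary result and costs almost nothing.

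**What to change.** In Sections 9.1.1 and 13.1, state that:

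- the primary ORR denominator is all participants who received at least one dose of ponatinib;
- those without a qualifying confirmed response count as non-responders;
- a confirmed response counts even if less than one cycle was received;
- the rule of at least 4 responders applies to 20 treated participants, and treated participants are not replaced;
- registered participants who never receive drug do not count toward the 20. Sections 4.1 and 4.3 foresee such cases, so 20 enrolled need not equal 20 treated;
- the 9.1.1 evaluable set is kept as a supportive analysis.

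The cost is a few sentences. No further treated participants or assessments are needed, although each untreated registrant means one more registration to reach 20 treated. The reported ORR may be slightly lower than on the 9.1.1 set.

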#### 9.1.2 Disease Parameters

Measurable disease. Measurable disease is the presence of at least one (1) lesion that can be accurately measured in at least one dimension with longest diameter  $\geq 20$  millimeters (mm) using conventional techniques (x-ray) or  $\geq 10$  mm with spiral CT scan. Measurable lesions must be at least 2 times the slice thickness in mm. All tumor measurements must be recorded in millimeters (or decimal fractions of centimeters).

**Note:** A lesion in a previously irradiated area is not eligible for measurable disease unless there is objective evidence of progression of the lesion prior to study enrollment. Lesions in previously irradiated areas must be clearly identified as such.

Malignant lymph nodes. To be considered pathologically enlarged and measurable, a lymph node must be  $\geq 15$  mm in short axis when assessed by CT scan (CT scan slice

thickness recommended to be no greater than 5 mm). At baseline and in follow-up, only the short axis will be measured and followed.

**Non-measurable disease.** All other lesions (or sites of disease), including small lesions (longest diameter < 10 mm or pathological lymph nodes with  $\geq$  10 to < 15 mm short axis), are considered non-measurable disease. Bone lesions, leptomeningeal disease, ascites, pleural/pericardial effusions, lymphangitis cutis/pulmonis, inflammatory breast disease, abdominal masses identified by physical exam that are not measurable by reproducible imaging techniques, and cystic lesions are all considered non-measurable.

**Target lesions.** All measurable lesions up to a maximum of 2 lesions per organ and 5 lesions in total, representative of all involved organs, should be identified as target lesions and recorded and measured at baseline. Lesions must be accurately measured in 1 dimension with a minimum size of 10 mm by CT or MRI (slice thickness no greater than 5 mm), 20 mm by *chest x-ray*. Nodes must have a short axis  $\geq$  15 mm. The short axis should be included in the sum of the lesions in the calculation of response. Nodes that shrink to < 10 mm are considered normal. Target lesions should be selected on the basis of their size, be representative of all the involved organs, and should be lesions that can be followed with reproducible repeated measurements.

Lytic bone lesions or mixed lytic-blastic lesions, *with identifiable soft tissue components*, that can be evaluated by cross sectional imaging techniques such as CT or MRI can be considered target lesions if the *soft tissue component* meets the definition of measurability as defined above. Cystic lesions thought to represent cystic metastases can be considered as target lesions. However, if non-cystic lesions are present, these are preferred for selection as target lesions. Lesions in previously irradiated areas or areas subject to other loco-regional therapy are usually not considered measurable unless there has been demonstrated progression of that lesion.

**Non-target lesions.** All other lesions, including small lesions < 10 mm or pathological lymph nodes measuring  $\geq$  10 mm to < 15 mm in short axis, as well as truly non-measurable lesions, which include leptomeningeal disease, ascites, pleural or pericardial effusion, inflammatory breast disease, lymphangitic involvement of skin or lung, abdominal masses identified by physical exam that are not measurable by reproducible imaging techniques.

### **Methods for Evaluation of Measurable Disease**

All measurements should be taken and recorded in metric notation, using a ruler, calipers, or digital measurement tool. All baseline evaluations should be performed as closely as possible to the beginning of treatment and never more than 14 days before the beginning of the treatment.

The same method of assessment and the same technique should be used to characterize each identified and reported lesion at baseline and during follow-up. Imaging-based

evaluation is preferred to evaluation by clinical examination when both methods have been used to assess the anti-tumor effect of a treatment.

**Clinical lesions.** Clinical lesions will only be considered measurable when they are superficial (e.g., skin nodules and palpable lymph nodes). For the case of skin lesions, documentation by color photography, including a ruler to estimate the size of the lesion, is recommended.

**Conventional CT and MRI.** These techniques should be performed with cuts of 10 mm or less in slice thickness contiguously. Spiral CT should be performed using a 5 mm contiguous reconstruction algorithm. This applies to tumors of the chest, abdomen, and pelvis. Head and neck tumors and those of extremities usually require specific protocols.

**FDG PET and PET/CT.** The acquisition of FDG PET and FDG PET/CT scans should follow the NCI Guidelines for using FDG PET as an indicator of therapeutic response (L.K. Shankar, J.M. Hoffman, S. Bacharach, M.M. Graham, J. Karp, A.A. Lammertsma, S. Larson, D.A. Mankoff, B.A. Siegel, A. Van den Abbeele, J. Yap, D. Sullivan. Consensus recommendations for the use of 18F-FDG PET as an indicator of therapeutic response in patients in National Cancer Institute Trials. *J Nucl Med*, 47(6):901-903, 2006). Participants should avoid strenuous exercise and be on a low carbohydrate diet for 24 hours prior to the scan. Participants should fast for 4 hours or longer prior to the FDG injection and should have a serum glucose of less than 200 mg/dL at the time of FDG injection. A 10-20 mCi dose of FDG should be injected for typical adult patients. For longitudinal studies with multiple scans, particular attention should be paid to ensure consistent patient preparation and acquisition parameters between the follow-up scan and the baseline scan. When designing a study where PET scans are going to be utilized as one of the modalities to evaluate efficacy, it is important to consult with physicians in nuclear medicine in designing the appropriate criteria to be utilized.

### **9.1.3 Response Criteria**

#### ***Evaluation of Target Lesions***

**Complete Response (CR):** Disappearance of all target lesions. Any pathological lymph node must have reduction in short axis to < 10 mm.

**Partial Response (PR):** At least a 30% decrease in the sum of the diameters of target lesions, taking as reference the baseline sum diameters.

**Progressive Disease (PD):** At least a 20% increase in the sum of the diameters of target lesions, taking as reference the smallest sum on study with at least a 5 mm absolute increase in the sum of all lesions. The appearance of one or more new lesions\* denotes disease progression.

Stable Disease (SD): Neither sufficient shrinkage to qualify for PR nor sufficient increase to qualify for PD, taking as reference the smallest sum diameters while on study.

Unknown (UN): Assessment of target lesions cannot be made due to insufficient or unevaluable data. In this case, a concise explanation must be given.

**Note:** If tumor response data is missing for target lesions, the overall assessment must be UN unless there is new disease that would result in an overall assessment of PD. However, if there is missing or unevaluable data for non-target lesions, but data is available for all target lesions, the overall response for that time point will be assigned based on the sum LD of all target lesions. Additionally, the assessment of CR cannot be made if there is missing or unevaluable data for non-target lesions. In this case, the overall assessment would be PR.

**\*Definition of New Lesion:** The finding of a new lesion should be unequivocal (i.e. not due to difference in scanning technique, imaging modality, or findings thought to represent something other than tumor (ex: new bone lesions may be healing or flare of pre-existing lesions)). However, a lesion identified on a follow-up scan in an anatomical location that was not scanned at baseline is considered new and will indicate PD. If a new lesion is equivocal (because of small size, etc.), follow-up evaluation will clarify if it truly represents new disease and if PD is confirmed, progression should be declared using the date of the initial scan on which the lesion was discovered.

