#### *Evaluation of Non-Target Lesions*

Complete Response (CR): Disappearance of all non-target lesions and normalization of tumor marker level. All lymph nodes must be non-pathological in size (< 10 mm short axis).

Incomplete Response/Stable Disease (SD): Persistence of one or more non-target lesions and/or maintenance of tumor marker level above the normal limits.

Progressive Disease (PD): Appearance of one or more new lesions\* (new lesions must be > slice thickness) and/or unequivocal progression of existing non-target lesions.

Overall level of substantial worsening that merits discontinuation of therapy. A useful test that can be applied when assessing non-targets for unequivocal progression is to consider if the increase in overall disease burden based on the change in non-measurable disease is comparable in magnitude to the increase that would be required to declare PD for measurable disease.

Unknown (UN): Assessment of non-target lesions cannot be made due to insufficient or unevaluable data. In this case, a concise explanation must be given.

**\*Definition of New Lesion:** The finding of a new lesion should be unequivocal (i.e. not due to difference in scanning technique, imaging modality, or findings thought to represent something other than tumor (ex: new bone lesions may be healing or flare of pre-existing lesions). However, a lesion identified on a follow-up scan in an anatomical location that was not scanned at baseline is considered new and will indicate PD. If a new lesion is equivocal (because of small size, etc.), follow-up evaluation will clarify if it truly represents new disease and if PD is confirmed, progression should be declared using the date of the initial scan on which the lesion was discovered.

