### ***Evaluation of Best Overall Response***

The best overall response is the best response recorded from the start of the treatment until disease progression/recurrence (taking as reference for progressive disease the smallest measurements recorded since the treatment started). The participant's best response assignment will depend on the achievement of both measurement and confirmation criteria.

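### Section 9.1.3 gives two answers, UN and PD, for a scan with missing target-lesion data, unequivocal non-target progression and no new lesion

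*Combined protocol and SAP*

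**What the plan says.** Three parts of Section 9.1.3 bear on this case.

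- **Evaluation of Target Lesions.** The target status UN applies when "Assessment of target lesions cannot be made due to insufficient or unevaluable data". The Note that follows sets the overall assessment: "If tumor response data is missing for target lesions, the overall assessment must be UN unless there is new disease". New disease is the only exception it names.
- **Evaluation of Non-Target Lesions.** PD is the appearance of new lesions "and/or unequivocal progression of existing non-target lesions". Growth of existing non-target disease is thus a route to PD of its own, listed apart from new lesions.
- **Response table for participants with measurable disease.** One row, in the order target, non-target, new lesions, overall response, reads "Any PD* Yes or No PD". Its footnote says: "In exceptional circumstances, unequivocal progression in non-target lesions may be accepted as disease progression". The table has no row for a target status of UN.

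Two further rules determine what follows. Under Evaluation of Best Overall Response, "The best overall response is the best response recorded from the start of the treatment until disease progression/recurrence". Section 1.5 defines PFS as running from study entry to progression or death.

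**The concern.** Suppose the target lesions were not assessed at a time point, existing non-target lesions have unequivocally progressed, and no new lesion is seen. The Note says UN and the table says PD. Two central readers could both follow the protocol and record different results.

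The case can arise in this trial. Section 3.2.2 admits participants with stable brain metastases, including asymptomatic ones under observation. Section 5.1, item 18, does not require routine follow-up brain imaging when there are no findings. A brain scan prompted by symptoms that shows growth of known non-target lesions, with no body imaging at that time point, fits the description.

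The error runs in one direction. Scoring UN can postpone or drop a progression but cannot create one. Section 9.1.6 gives the RECIST determination to central review, while outside sites act on their own reads, so a site may act on progression at a scan that is centrally recorded as unknown. Section 13.3.2 has no rule for UN scans in the PFS analysis.

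**Working it through.** **Step 1: the plan's own figure.** Section 13.1 declares promise if at least 4 of 20 participants respond, with null rate 10% and alternative 30%. With X binomial (20, p), P(X ≥ 4) = 1 − Σ C(20,k) p^k (1 − p)^(20 − k), summed over k = 0 to 3.

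- p = 0.30: 0.8929, against the stated 89%.
- p = 0.10: 0.1330, against the stated 13%.

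Both reproduce. Neither depends on how UN and PD are told apart at a scan, because neither is a response.

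**Step 2: score every combination with target data missing.** Four non-target statuses times new lesion yes or no gives 4 × 2 = 8.

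| Non-target status | New lesion | Note | Table | Agree? |
|---|---|---|---|---|
| CR | Yes | PD | PD | yes |
| Non-CR/Non-PD | Yes | PD | PD | yes |
| Not evaluated | Yes | PD | PD | yes |
| PD | Yes | PD | PD | yes |
| CR | No | UN | no row | no direct conflict |
| Non-CR/Non-PD | No | UN | no row | no direct conflict |
| Not evaluated | No | UN | no row | no direct conflict |
| PD | No | UN | PD (footnoted) | **conflict** |

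Four combinations agree, three are covered by the Note alone, and one is contradictory. Reconciling the two rules brings the count from 1 to 0.

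**Step 3: does the table's Any include missing target data?** Section 9.1.3 lists UN as a target status. The Note's own exception (target missing, new disease, overall PD) matches the table's row for any target status, any non-target status and a new lesion only if Any covers missing data. The same word in the row above should mean the same thing.

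**Step 4: effect on timing.** Table 8-1, footnote 8, sets scans at 8-week intervals, then 12-week intervals from cycle 11. If the affected scan is UN and the next scheduled scan is complete and shows PD, the PFS date moves by about 8 × 7 = 56 days, or 12 × 7 = 84 days from cycle 11. An earlier scan or a death shortens this. Section 5.1, item 18, requires imaging at End of Treatment, and Section 5.5 puts those procedures within 14 days of the last dose. A participant who stops treatment at the affected scan may therefore be imaged well inside 56 days.

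**Step 5: partly measured target sets.** The Note does not clearly say whether one unmeasured lesion makes target data missing. Diameters cannot be negative, so if the measured lesions alone are at least 20% and 5 mm above the smallest sum, the missing lesion cannot undo PD. Hypothetical example: the smallest sum is 60 mm (three lesions of 20 mm), and two lesions now measure 38 + 36 = 74 mm. The threshold is 60 × 1.2 = 72 mm and the increase is at least 74 − 60 = 14 mm. PD is certain, yet a literal reader of the Note could record UN.

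**The case against.** The strongest reply is that the table does not require PD. Its row carries a footnote that only permits progression to be accepted, and only exceptionally. That stands: PD in this row is discretionary. It does not remove the conflict, because the Note forbids what the footnote allows, and the footnote is silent on missing target data.

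New disease might also be stretched to cover growth of existing non-target lesions. The non-target definition lists the two separately, so the text does not support that.

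The partly measured case is not a contradiction between passages. UN as a target status applies when no assessment can be made; if the measured lesions already meet the PD criteria, one arguably can be. This is an ambiguity, and it calls for clarification only.

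A reader might infer that every affected scan costs at least one full interval of PFS, and that the event is lost once another therapy starts. The documents do not support either. End of Treatment imaging can come sooner, and death is a PFS event under Section 1.5 (although Section 9.1.5 names only objective progression). Sections 5.7 and 5.8 continue PFS follow-up to 2 years, and the note under the response table asks for efforts to document progression after treatment stops. What remains is narrower: Section 5.7 schedules tumor scans only for those who stopped for reasons other than progression, and only until new therapy, so a late or missed date is possible but not assured.

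A reader might also infer that response rates are inflated because the best-response window stays open. That would need a later, confirmed CR or PR. The table's CR and PR rows exclude non-target PD, so the progression would first have to reverse.

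**Conclusion.** The contradiction is real but narrow: one of the 8 combinations with target data missing, with no rule of precedence. Applying the Note would score a real progression as UN. The consequence is a PFS date that may be late by up to about one scan interval, or an event that may be missed, together with UN in place of PD as best response. The timing figure assumes that the next scheduled scan is complete.

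The weight is limited. Section 13.3 makes the secondary endpoints exploratory. The documents give no frequency for the scenario. An assumed 0 to 2 participants of 20 is only a guess, and the range includes none; each participant would be 1/20 = 5% of the sample.

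The primary analysis is unaffected. One could imagine UN participants being dropped from the response denominator with the cut-off kept at 4, giving power 0.867 and type I error 0.115 at n = 19, or 0.835 and 0.098 at n = 18. The documents do not say that UN participants are excluded, so this is not part of the finding.

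The wording should be corrected because the correction is nearly free, but it does not threaten the trial's main conclusion.

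**What to change.** Reconcile the Note with the table before central reads. For example: *the overall assessment is UN unless there is a new lesion or unequivocal progression of non-target lesions (as in the table and its footnote), in which case it is PD.* Keeping the reference to the footnote preserves its discretion; the reading instruction should say how the central reader applies it.

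As a clarification, add that a partly measured target set is PD when the measured lesions alone already meet the PD criteria, at least 20% and 5 mm above the smallest sum.

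The cost is a sentence or two in Section 9.1.3 and a matching instruction to the central imaging core. No scans are added, and sample size, power and type I error stay as they are. Settling it before reads matters because a later choice would be made with the data in view.
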